#### 4.1. Protocol Deviations

Important protocol deviations (including deviations related to study inclusion/exclusion criteria, conduct of the trial, participant management or participant assessment) will be summarized and listed.

Protocol deviations will be tracked by the study team throughout the conduct of the study in accordance with the Protocol Deviation Management Plan. The "significant" protocol deviation in the Protocol Deviation Management Plan is equivalent to "important" protocol deviations.

- Data will be reviewed prior to freezing the database to ensure all significant deviations and deviations which may lead to exclusion from the analysis are captured and categorised on the protocol deviations dataset.
- This dataset will be the basis for the summaries and listings of protocol deviations.

A separate listing of all inclusion/exclusion criteria deviations will also be provided. This listing will be based on data as recorded on the inclusion/exclusion page of the electronic case record form (eCRF).

# 5. CONSIDERATIONS FOR DATA ANALYSES AND DATA HANDLING CONVENTIONS

# 5.1. Study Treatment & Sub-group Display Descriptors

Treatment Group Descriptions					
Data Displays for Reporting					
Description Code Order in TI					
Portia (0.03 mg EE/0.15 mg LNG) QD on Days -3 to -1	Run-in Portia	1			
Portia (0.03 mg EE/0.15 mg LNG) QD on Days 1 to 10	Treatment A	2			
Portia (0.03 mg EE/0.15 mg LNG) QD coadministered with GSK3640254 200 mg on Days 11 to 21	Treatment B	3			

#### 5.2. Baseline Definitions

For all endpoints (except as noted in baseline definitions), baseline for treatment A is defined as the latest pre-dose assessment with a non-missing value, including those from unscheduled visits, before the dose of Portia on Day 1; baseline for treatment B is defined as the latest pre-dose assessment with a non-missing value, including those from unscheduled visits, before the first dose on Day 11. If time is not collected, Day 1 or Day 11 assessments are assumed to be taken prior to the dose and used as baseline.

Parameter	Study Assessments Considered as Baseline				Baseline Used in Data Display		
	Screening	Day - 4	Day 1 (Pre- Dose)	Day 10	Day 11 (Pre- Dose)	Treatment A	Treatment B
Safety							
Vital Sign	Х	Х	Х	Х	Х	Day 1 (Pre- Dose)[1]	Day 11 (Pre- Dose) 
12-Lead ECG	Х	Х	Х	Х	Х	Day 1 (Pre- Dose)	Day 11 (Pre- Dose) 
Hematology	Х	Х	Х	Х		Day 1 (Pre- Dose)	Day 10
Clinical Chemistry	Х	Х	Х	Х		Day 1 (Pre- Dose)	Day 10
Urinalysis	Х	Х	Х	Х		Day 1 (Pre- Dose)	Day 10

 The average (for quantitative assessments) or the worst case (for interpretation) of the predose triplicate assessments will be used as the baseline.

Unless otherwise stated, if baseline data is missing no derivation will be performed and baseline will be set to missing.

# 5.3. Other Considerations for Data Analyses and Data Handling Conventions

Other considerations for data analyses and data handling conventions are outlined in the appendices:

Section	Component
11.1	Appendix 1: Schedule of Activities
11.2	Appendix 2: Study Phases and Treatment Emergent Adverse Events
11.3	Appendix 3: Data Display Standards & Handling Conventions
11.4	Appendix 4: Derived and Transformed Data
11.5	Appendix 5: Reporting Standards for Missing Data
11.6	Appendix 6: Division of AIDS (DAIDS) Table for Grading the Severity of Adult and Pediatric Adverse Events
11.7	Appendix 7: Values of Potential Clinical Importance

# 6. STUDY POPULATION ANALYSES

# 6.1. Overview of Planned Study Population Analyses

The study population analyses will be based on the "Safety" or "Screened" population, unless otherwise specified.

Study population analyses including analyses of participant's disposition, protocol deviations (including inclusion/exclusion criteria deviations), demographic and baseline characteristics, prior and concomitant medications, and exposure will be based on GSK Core Data Standards. Details of the planned displays are presented in Appendix 9: List of Data Displays.

#### 7. PHARMACOKINETIC ANALYSES

## 7.1. Primary Pharmacokinetic Analyses

#### 7.1.1. Endpoint / Variables

#### 7.1.1.1. Drug Concentration Measures

Refer to Appendix 3: Data Display Standards & Handling Conventions (Section 11.3.3 Reporting Standards for Pharmacokinetics). Plasma concentrations of EE, LNG, and GSK3640254 will be measured and reported.

#### 7.1.1.2. Derived Pharmacokinetic Parameters

Pharmacokinetic parameters will be calculated by standard non-compartmental analysis according to current working practices and using the currently supported version of WinNonlin (8.0 or higher). All calculations of non-compartmental parameters will be based on actual sampling times. Pharmacokinetic parameters listed will be determined from the plasma concentration-time data, as data permits.

Parameter	Parameter Description
Cmax	Maximum observed concentration, determined directly from the concentration-time data.
Сτ	Plasma concentration at the end of the dosing interval
AUC(0-τ)	Area under the plasma concentration-time curve from time 0 to the end of the dosing
	interval at steady state, to be calculated using the linear trapezoidal rule for each
	incremental trapezoid and the log trapezoidal rule for each decremental trapezoid.

#### NOTES:

Additional parameters may be included as required.

#### 7.1.2. Summary Measure

AUC(0- $\tau$ ), C $\tau$  and Cmax at steady state following doses of 0.03 mg EE/0.15 mg LNG QD Days 1 through 10 in Treatment A and 0.03 mg EE/0.15 mg LNG QD coadministered with GSK3640254 200 mg QD on Days 11 through 21 in Treatment B in healthy female subjects.

#### 7.1.3. Population of Interest

The primary PK analyses will be based on the PK concentration population for plasma PK concentrations and the PK parameter population for plasma PK parameters and statistical analysis.

# 7.1.4. Statistical Analyses / Methods

Details of the planned displays are provided in Appendix 9: List of Data Displays and will be based on GSK Data Standards and statistical principles.

Unless otherwise specified, endpoints / variables defined in Section 7.1.1 will be summarized using descriptive statistics, graphically presented (where appropriate) and listed.

Primary plasma PK parameters (AUC(0- $\tau$ ), C $\tau$ , and Cmax) will be estimated for EE and LNG (Treatments A and B). Summary statistics (arithmetic mean, geometric mean, median, standard deviation (SD), minimum, maximum, and coefficient of variation) for plasma EE and LNG PK parameter values will be summarized by treatment.

Boxplots with overlaid individual values of primary plasma PK parameters for EE and LNG will be produced for subjects categorized by ALT (ALT level within normal range, ALT value is greater than upper limit of normal [ULN] but less than or equal to 3 times the ULN, and ALT level is greater than 3 times the ULN) and whether subjects met liver stopping criteria. Similarly, boxplots with overlaid individual values of primary plasma PK parameters will be produced by treatment with data presented according to subject's progesterone level (progesterone level is less than or equal to 6.36 nmol/L and progesterone level is greater than to 6.36 nmol/L) and whether subjects met liver stopping criteria.

## 7.1.4.1. Statistical Methodology Specification

The following PK statistical analyses will only be performed if sufficient data are available (i.e. if participants have well defined plasma profiles).

#### **Endpoint / Variables**

• Plasma primary PK endpoints include AUC(0- $\tau$ ), C $\tau$ , and Cmax for EE and LNG (Treatments A and B), as data permit

#### **Model Specification**

- Analyses will be performed on the natural logarithms of AUC(0-τ), Cτ and Cmax using linear mixed-effect models with treatment as a fixed effect, participants as random effect, and measurements within participant as repeated measures.
- Effects will be estimated, and confidence intervals (CIs) will be constructed for the following treatment comparisons:
  - Treatment B versus Treatment A
- Point estimates and 90% CIs for treatment differences on the log scale derived from the model will be exponentiated to obtain estimates for geometric mean ratios and CIs on the original scale.

#### **Model Checking & Diagnostics**

 Model assumptions will be applied, but appropriate adjustments may be made based on the data.

#### **Model Results Presentation**

- Statistical analysis by analysis of variance (ANOVA) will be presented in tabular format with geometric mean ratios for:
  - Treatment B versus Treatment A

#### 7.2. Secondary Pharmacokinetic Analyses

#### 7.2.1. Endpoint / Variables

#### 7.2.1.1. Drug Concentration Measures

Refer to Appendix 3: Data Display Standards & Handling Conventions (Section 11.3.3 Reporting Standards for Pharmacokinetic).

#### 7.2.1.2. Derived Pharmacokinetic Parameters

Pharmacokinetic parameters will be calculated by standard non-compartmental analysis according to current working practices and using the currently supported version of WinNonlin (8.0 or higher). All calculations of non-compartmental parameters will be based on actual sampling times.

Plasma pharmacokinetic parameters listed below will be determined from the total plasma concentration-time data, as data permits.

Parameter	Parameter Description
Cmax	Maximum observed concentration, determined directly from the concentration-time data.
	(GSK3640254 only)
Ст	Plasma concentration at the end of the dosing interval (GSK3640254 only)
AUC(0-t)	Area under the plasma concentration-time curve from time 0 to the end of the dosing interval at steady state, to be calculated using the linear trapezoidal rule for each incremental trapezoid and the log trapezoidal rule for each decremental trapezoid. (GSK3640254 only)
Tmax	Time of maximum observed concentration
t1/2	Apparent terminal phase half-life

#### NOTES:

Additional parameters may be included as required.

#### 7.2.2. Summary Measure

Ethinyl estradiol and LNG Tmax, and t1/2 at steady state following doses of 0.03 mg EE/0.15 mg LNG QD Days 1 through 10 in Treatment A and 0.03 mg EE/0.15 mg LNG QD coadministered with GSK3640254 200 mg QD on Days 11 through 21 in Treatment B in healthy female subjects.

GSK3640254 AUC(0-τ), Cτ, Cmax, Tmax, and t1/2 at steady state following doses of 0.03 mg EE/0.15 mg LNG QD coadministered with GSK3640254 200 mg QD on Days 11 through 21 in Treatment B in healthy female subjects.

#### 7.2.3. Population of Interest

The secondary PK analyses will be based on the PK concentration population for plasma PK concentrations, and the PK parameter population for plasma and statistical analysis, unless otherwise specified.

#### 7.2.4. Statistical Analyses / Methods

Details of the planned displays are provided in Appendix 9: List of Data Displays and statistical principles.

Unless otherwise specified, endpoints/variables defined in Section 7.2.1 will be summarized using descriptive statistics, graphically presented (where appropriate), and listed.

Secondary plasma PK parameters (Tmax and t1/2) will be estimated for EE and LNG (Treatments A and B) and secondary plasma PK parameters AUC(0- $\tau$ ), C $\tau$ , Cmax, Tmax, and t1/2 will be estimated for GSK3640254 (Treatment B). Summary statistics (arithmetic mean, geometric mean, median, SD, minimum, maximum, and coefficient of variation) for secondary plasma PK parameters of GSK3640254 and EE and LNG will be summarized by treatment.

Predose (trough) PK plasma concentrations (EE and LNG: Days 9, 10, 11 [Treatment A], 19 through 21 and the 24-hour post-Day 21 dose [Treatment B]; GSK3640254: Days 19 through 21 and the 24-hour post-Day 21 dose [Treatment B]) will be summarized using the PK Concentration Population and used to assess achievement of steady state.

Boxplots with overlaid individual values of primary plasma PK parameters for GSK3640254 will be produced for subjects categorized by ALT (ALT level within normal range, ALT value is greater than upper limit of normal [ULN] but less than or equal to 3 times the ULN, and ALT level is greater than 3 times the ULN) and whether subjects met liver stopping criteria. Similarly, boxplots with overlaid individual values of primary plasma PK parameters will be produced by treatment with data presented according to subject's progesterone level (progesterone level is less than or equal to 6.36 nmol/L and progesterone level is greater than to 6.36 nmol/L) and whether subjects met liver stopping criteria.

#### 8. PHARMACODYNAMIC ANALYSES

## 8.1. Endpoint / Variables

Serum LH, FSH, and progesterone levels when EE/LNG is administered alone and in combination with GSK3640254.

### 8.2. Summary Measures

Serum LH, FSH, and progesterone levels.

### 8.3. Population of Interest

The PD analyses will be based on the "Pharmacodynamic Concentration" population, unless otherwise specified.

## 8.4. Statistical Analysis / Methods

Details of the planned displays are provided in Appendix 9: List of Data Displays and will be based on GSK Data Standards and statistical principles.

Individual concentration-time profiles will be created for LH, FSH and progesterone. For each parameter, the profiles for both treatments will be overlaid on the same plot.

Actual values for serum LH, FSH, and progesterone levels will be listed and summarized by treatment using descriptive statistics; in addition, the mean value with the SD will be presented in a figure. The maximum LH and FSH concentration of each treatment period will be identified for each subject and listed with treatment and day and summarized by treatment.

For each parameter (LH, FSH, and progesterone), the concentrations will be plotted by treatment and timepoint using box-plots displaying the median, range, 25th and 75th percentiles. Maximum LH and FSH will be plotted within the same figure.

#### 9. SAFETY ANALYSES

The safety analyses will be based on the "Safety" population unless otherwise specified.

#### 9.1. Adverse Events Analyses

Adverse events analyses including the analysis of AEs, SAEs, AEs of special interest, and other significant AEs will be based on GSK Core Data Standards. The details of the planned displays are provided in Appendix 9: List of Data Displays.

#### 9.2. Clinical Laboratory Analyses

Laboratory evaluations including the analyses of chemistry laboratory tests, hematology laboratory tests, urinalysis, liver function tests, and pregnancy test will be based on GSK Core Data Standards and will be graded using the Division of AIDS (DAIDS) Table for Grading the Severity of Adult and Pediatric Adverse Events (Version 2.1, July 2017). Alanine aminotransferase, aspartate aminotransferase, alkaline phosphatase, total bilirubin, and gamma-glutamyl transferase will be plotted versus time. The details of the planned displays are in Appendix 9: List of Data Displays.

#### 9.3. Other Safety Analyses

The analyses of non-laboratory safety test results including ECGs, vital signs, liver events, and Columbia Suicide Severity Rating Scale (C-SSRS) will be based on GSK Core Data Standards, unless otherwise specified. A figure of mean change from baseline in QTcF interval along with the 2-sided 95% CI using Student's t distribution will be presented by treatment and visit. The details of the planned displays are presented in Appendix 9: List of Data Displays.

# 11. APPENDICES

# 11.1. Appendix 1: Schedule of Activities

# 11.1.1. Protocol Defined Schedule of Events

# **Screening Visit**

Procedure	Screening (up to 28 days before Day -4)
Outpatient visit	X
Informed consent	X
Inclusion and exclusion criteria	X
Demography	X
Full physical examination including height and weight 	X
Laboratory assessments (hematology, chemistry, urinalysis)	X
12-lead electrocardiogram (ECG)	X
Vital sign measurements	X
Medication/drug/alcohol history	X
Past and current medical conditions	X
Columbia Suicide Severity Rating Scale (C-SSRS)	X
Serum pregnancy test	X
Drug, alcohol, and cotinine screen	X
Human immunodeficiency virus (HIV), Hepatitis B and C screening	X

<sup>1. A full physical examination will include at a minimum, assessments of the skin, cardiovascular, respiratory, gastrointestinal (GI), and neurological systems.

Table 2 Time and Events Table

Procedure	Check-in		Run-ir	1				_	Tre	eatmen	t					Wash	nout 1		Notes
	D -4	D -3	D -2	D -1	D 1	D 2-9	D 10 	D 11	D 12	D 13	D 14-18	D 19	D 20	D 21	D 22	D 23	D 24 	D 25	
Admit to clinic	Х																		
Discharge from clinic																		Χ	
Brief physical examination	Х						х										Х		A brief physical examination will include, at a minimum, assessments of the skin, lungs, cardiovascular system, and abdomen (liver and spleen.
Vital signs	Х				Х		х	Х			D15			Х			Х		Obtained before dosing, where applicable. Blood pressure and pulse will be measured in triplicate when they occur at the same time point as clinical laboratory assessments.
12-lead ECG	Х				Х		Х	х			D15			Х			Х		On Day 11, triplicate ECGs will be taken before dosing. On Day 11, single ECGs will be taken at 2, 4, and 6 hours after dosing. On Day 15, single ECGs will be taken at 2, 4, and 6 hours after dosing. Single ECGs will be taken on other scheduled days.

Procedure	Check-in	ı	Run-ir	1					Tre	eatmen	t					Wash	nout 1		Notes
	D -4	D -3	D -2	D -1	D 1	D 2-9	D 10 	D 11	D 12	D 13	D 14-18	D 19	D 20	D 21	D 22	D 23	D 24 	D 25	
Drug, alcohol, and cotinine screen	Х																		See Protocol Appendix 2 for specific tests to be performed.
Laboratory assessments (hematology, chemistry, urinalysis tests)	Х				Х		Х							х			х		See Protocol Appendix 2 for specific tests to be performed. Taken before dosing, where applicable.
Pregnancy test	Х			Χ			Χ										Х		
Genetic sample (optional)	Х																		
C-SSRS								Χ						Х					
Study intervention: Portia (0.03 mg EE/ 0.15 mg LNG)		Х	Х	Х	Х	Х	Х	Х	Х	Х	Х	Х	Х	Х					
Study intervention: GSK3640254 200 mg								Χ	Х	Х	Х	Х	Х	Х					
Trough PK sampling: EE and LNG						D9						Х	Х						PK sample collected before dosing.

Procedure	Check-in	I	Run-ir	1					Tre	eatmen	t					Wash	out 1		Notes
	D -4	D -3	D -2	D -1	D 1	D 2-9	D 10 	D 11	D 12	D 13	D 14-18	D 19	D 20	D 21	D 22	D 23	D 24 	D 25	
Serial PK sampling: EE and LNG							X	Х						X	X	X	X		PK samples will be collected predose and after dosing at 15 and 30 minutes and 1, 1.5, 2, 3, 4, 7, 12, and 24 hours relative to Day 10 dosing. The 24-hour post-dose sample should be taken prior to dosing on Day 11. PK samples will be collected predose and after dosing at 15 and 30 minutes and 1, 1.5, 2, 3, 4, 7, 12, 24, 48, and 72 hours relative to Day 21 dosing.
Trough PK sampling: GSK3640254												Χ	Χ						PK sample collected before dosing.
Serial PK sampling: GSK3640254														Х	Х	Х	X	Х	PK samples will be collected predose and after dosing at 1, 2, 2.5, 3, 3.5, 4, 4.5, 5, 6, 8, 12, 24, 48, 72, and 96 hours relative to Day 21 dosing.
PD sampling: LH, FSH, progesterone					Χ		Х	Х						Х	Х				Samples collected before dosing.
AE review		←====================================								====									
SAE review	←====	====	====	=====	====	=====	=====	====	====	=====	======	=====	=====	=====	=====	=====	=====	==>	

Procedure	Check-in		Run-ir	1		Treatment										Wasl	nout 1		Notes
	D -4	D -3	D -2	D -1	D 1	D 2-9	D 10 	D 11	D 12	D 13	D 14-18	D 19	D 20	D 21	D 22	D 23	D 24 	D 25	
Concomitant medication review	←====		=====		====	=====		====	====	=====	======	=====	====	=====	=====		=====	==>	

AE = adverse event; D = Day; C-SSRS = Columbia Suicide Severity Rating Scale; ECG = electrocardiogram; EE = ethinyl estradiol; FSH = follicle-stimulating hormone; LH = luteinizing hormone; LNG = levonorgestrel; PD = pharmacodynamic; PK = pharmacokinetic; SAE = serious adverse event.

- 1 Washout period refers to follow-up period. See 208135 Protocol Clarification dated 10-Jun-2019.
- 2 Assessments performed on Day 10 will be considered Baseline for GSK3640254 dosing.
- 3 Evaluations scheduled for Day 24 will also be performed for participants who discontinue early.

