# 2.2. Study Objective(s) and Endpoint(s)

[figure not shown]
Objectives	Endpoints
Primary Objectives	Primary Endpoints
To assess the effect of GSK3640254 on the steady state PK of EE and LNG under fed conditions in healthy female participants	• AUC(0- $\tau$ ), Cmax, and C $\tau$ for EE and LNG
Secondary Objectives	Secondary Endpoints
To assess the effect of GSK3640254 on the PD of EE/LNG (suppression of ovulation as indicated by endogenous progesterone levels)	Serum progesterone levels
To assess the effect of GSK3640254 on LH and FSH	Serum FSH and LH levels
To characterize the steady state PK of GSK3640254 in the presence of EE/LNG	• AUC(0-τ), Cmax, Cτ, Tmax, and t1/2 for GSK3640254
To Characterize the steady state PK of EE/LNG alone and in the presence of GSK3640254	Tmax and t1/2 for EE and LNG
To assess the safety and tolerability of GSK3640254 and EE/LNG when given in combination in healthy female participants	Safety and tolerability parameters for AEs/SAEs, observed and change from baseline clinical laboratory assessments, ECGs, and vital sign measurements

AE = adverse event; AUC(0- $\tau$ ) = area under the plasma concentration-time curve from time 0 to the end of the dosing interval at steady state; Cmax = maximum observed concentration; C $\tau$  = Plasma concentration at the end of the dosing

Objectives	Endpoints

interval; ECG = electrocardiogram; EE = ethinyl estradiol; FSH = follicle-stimulating hormone; LH = luteinizing hormone; LNG = levonorgestrel; PD = pharmacodynamic; PK = pharmacokinetic; SAE = serious adverse event; t1/2 = apparent terminal phase half-life; Tmax = time of maximum observed concentration.

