## 11.3.3. Reporting Standards for Pharmacokinetics

Pharmacokinetic Concentration Data						
Descriptive Summary	Refer to IDSL PK Display Standards.					
Statistics, Graphical	Refer to IDSL Statistical Principle 6.06.1.					
Displays and Listings	For continuous data:					
	
 
NQs at the beginning of a participant profile (i.e. before the first incidence of a measurable concentration) are deemed to be zero as it is assumed that in this circumstance no drug is yet measurable in the blood.
 
For NQs at the end of the participant profile (i.e. after the last incidence of a measurable concentration);
 
					
	
 
for individual plots and pharmacokinetic analyses these are dropped (set to missing) as they do not provide any useful information (and can erroneously indicate that absolutely no drug is present)
 
for summary statistics, these are set to 0 (to avoid skewing of the
 
					
	
 
summary statistics)
 
Individual NQs which fall between two measurable concentrations are set to missing (individual values of this nature are assumed to be an anomaly)
 
If two or more NQ values occur in succession between measurable concentrations, the profile will be deemed to have terminated at the last measurable concentration prior to these NQs. For the purpose of individual participant plots, these NQs will be set to 0, and the subsequent measurable concentrations will be retained. For the derivation of pharmacokinetic parameters, these NQs and any subsequent measurable concentrations will be omitted (set to missing).
 
Note: Concentration values will be imputed as per GUI_51487 for descriptive summary statistics/analysis and summarized graphical displays only.
 
					
Pharmacokinetic Para	ameter Data					
Descriptive Summary Statistics, Graphical Displays and Listings	N, n, arithmetic mean, 90% CI of arithmetic mean, geometric mean, 95% CI of geometric mean, SD, SD of logged data CV (%), and between-subject geometric coefficient of variation (CVb (%)) will be reported. $ \text{CV}_{\text{b}} \text{ ($\infty$)} = \sqrt{\left(\text{exp}(\text{SD}^2) - 1\right) * 100} $					

(SD = SD of Ln-Transformed data)

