#### CONFIDENTIAL

Parameters Not Being Ln- Transformed	Tmax, λz, λz lower, λz upper, and λz no. of points.
Parameters Not Being Summarized	λz, λz lower, λz upper, and λz no. of points.
Listings	Include the first point, last point and number of points used in the determination of λz and Rsq_adjusted for listings.

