### 11.9.7. Pharmacokinetic Tables

Pharm	Pharmacokinetic: Tables								
No.	Population	IDSL / Example Shell	Title	Programming Notes	Deliverable [Priority]				
PK Co	PK Concentration Data								
3.1.	PK Concentration	PKCT1	Summary of Ethinyl Estradiol (EE) Plasma Pharmacokinetic Concentration-Time Data (units) by Treatment		SAC				
3.2.	PK Concentration	PKCT1	Summary of Levonorgestrel (LNG) Plasma Pharmacokinetic Concentration-Time Data (units) by Treatment		SAC				
3.3.	PK Concentration	PKCT1	Summary of GSK3640254 Plasma Pharmacokinetic Concentration-Time Data (units) by Treatment		SAC				
3.4.	PK Concentration	PKCT1	Summary of Predose (trough) Ethinyl Estradiol (EE) Plasma Concentration Data (units) by Treatment		SAC				
3.5.	PK Concentration	PKCT1	Summary of Predose (trough) Levonorgestrel (LNG) Plasma Concentration Data (units) by Treatment		SAC				
3.6.	PK Concentration	PKCT1	Summary of Predose (trough) GSK3640254 Plasma Concentration Data (units) by Treatment		SAC				
PK Dei	rived Parameters	3							
3.7.	PK Parameter	PKPT4	Summary Statistics of Derived Ethinyl Estradiol (EE) Plasma Pharmacokinetic Parameters (Non-Transformed) Based on Actual Time by Treatment	Parameters with units	SAC				
3.8.	PK Parameter	PKPT4	Summary Statistics of Derived Ethinyl Estradiol (EE) Plasma Pharmacokinetic Parameters (Ln-Transformed) Based on Actual Time by Treatment	Parameters with units	SAC				
3.9.	PK Parameter	PKPT4	Summary Statistics of Derived Levonorgestrel (LNG) Plasma Pharmacokinetic Parameters (Non-Transformed) Based on Actual Time by Treatment	Parameters with units	SAC				
3.10.	PK Parameter	PKPT4	Summary Statistics of Derived Levonorgestrel (LNG) Plasma Pharmacokinetic Parameters (Ln-Transformed) Based on Actual Time by Treatment	Parameters with units	SAC				

Pharma	Pharmacokinetic: Tables							
No.	Population	IDSL / Example Shell	Title	Programming Notes	Deliverable [Priority]			
3.11.	PK Parameter	PKPT4	Summary Statistics of Derived GSK3640254 Plasma Pharmacokinetic Parameters (Non-Transformed) Based on Actual Time by Treatment	Parameters with units	SAC			
3.12.	PK Parameter	PKPT4	Summary Statistics of Derived GSK3640254 Plasma Pharmacokinetic Parameters (Ln-Transformed) Based on Actual Time by Treatment	Parameters with units	SAC			
PK Ana	lysis Tables							
3.13.	PK Parameter	PKPT3	Statistical Analysis of Ethinyl Estradiol (EE) Plasma Pharmacokinetic Parameters: Analysis of Variance (ANOVA)	AUC(0-τ), Cτ, and Cmax	SAC			

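### EE and LNG half-life is summarized for Treatments A and B, but sampling stops at 24 h in A and 72 h in B with no common λz window, so the two values may not be comparable

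*SAP*

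**What the plan says.** Section 2.2 lists a secondary objective, "To Characterize the steady state PK of EE/LNG alone and in the presence of GSK3640254", with Tmax and t1/2 of EE and LNG as its endpoints. Section 7.2.1.2 defines t1/2 only as "Apparent terminal phase half-life" and refers to non-compartmental analysis under current working practices. Sections 7.2.2 and 7.2.4 have it estimated for EE and LNG in both treatments and summarized by treatment. The displays are Tables 3.7 to 3.10 in Section 11.9.7.

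The schedule in Section 11.1.1 gives the two treatments different sampling lengths. Treatment A is sampled to "1, 1.5, 2, 3, 4, 7, 12, and 24 hours relative to Day 10 dosing", the last sample being taken before the Day 11 dose. Treatment B is sampled to "7, 12, 24, 48, and 72 hours relative to Day 21 dosing".

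The only provision on λz is in Section 11.3.3. It asks that listings "Include the first point, last point and number of points used in the determination of" λz, together with adjusted R-squared. The same section treats unquantifiable samples at the end of a profile as missing in the pharmacokinetic analysis. The SAP has no λz selection rule, no window common to the two treatments and no caveat on comparing them.

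**The concern.** t1/2 is ln 2 divided by λz, and λz is a regression slope whose value depends on which samples enter the fit. At or after 12 h, Treatment A has two samples (12 and 24 h) and Treatment B has four (12, 24, 48 and 72 h). With the customary minimum of three points (an assumption, since the SAP states none), the fit in A must reach back to 7 h or earlier. In B it can rest on 24, 48 and 72 h alone. If distribution is still contributing between 7 and 24 h, the slope in A is steeper and its half-life shorter, even when the drug behaves identically in both treatments.

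Two misreadings of Tables 3.7 to 3.10 are then possible. A reader may see a longer half-life with GSK3640254 and infer slower elimination that is not there. Or a real shortening, the direction that matters for a contraceptive, may be cancelled by the window difference and go unnoticed.

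**Working it through.** The SAP states no half-life for EE or LNG, so there is no figure of its own to reproduce. The check is an illustration under stated assumptions.

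**Inputs from the SAP**
- Sampling times from Section 11.1.1: predose, 0.25, 0.5, 1, 1.5, 2, 3, 4, 7, 12 and 24 h in A; the same plus 48 and 72 h in B.
- Daily dosing from Day -3. Day 10 is dose 3 + 10 = 13 and Day 21 is dose 13 + 11 = 24.

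**Assumed inputs (not in the SAP)**
- Absorption rate 1.5/h.
- Distribution half-life 1.5, 3 or 5 h; terminal half-life 16, 24 or 36 h; slow-phase coefficient f = 0.2, 0.35 or 0.5. This gives 3 × 3 × 3 = 27 scenarios.
- λz chosen by best adjusted R-squared with at least three points after Cmax; near-ties go to the longer window.
- No measurement error.

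**Model.** For n doses given 24 h apart, the concentration at time t after the last dose is

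C(t) = Σ over k = 0 to n−1 of { (1−f)[e^(−αs) − e^(−ka·s)] + f[e^(−βs) − e^(−ka·s)] }, with s = t + 24k,

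where α and β are ln 2 divided by the distribution and terminal half-lives. Then t1/2 = ln 2 / λz.

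**Mid-grid case** (distribution 3 h, terminal 24 h, f = 0.35, no drug effect)
- A, fitted on 7, 12 and 24 h: concentrations 0.7013, 0.5357 and 0.3525 (arbitrary units). The log-linear slope is −0.03943/h, so t1/2 = 0.6931 / 0.03943 = 17.6 h.
- B, fitted on 24, 48 and 72 h: concentrations 0.3525, 0.1750 and 0.0875. The slope is −0.02903/h, so t1/2 = 0.6931 / 0.02903 = 23.9 h.
- Ratio B/A = 23.9 / 17.6 = 1.36, although the kinetics are identical.

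**All 27 scenarios, no drug effect**

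| Samples available in B | B/A ratio of t1/2 | Median |
|---|---|---|
| To 72 h | 1.04 to 2.06 | 1.31 |
| 72 h unquantifiable and dropped | 1.04 to 1.60 | 1.21 |
| 48 and 72 h both dropped | 1.00 | 1.00 |

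The fitted window in A was 7 to 24 h in 27 of 27 scenarios. In B, with all samples, it was 24 to 72 h in 18 and 12 to 72 h in 9. With single-phase decline (terminal half-life 16, 24 or 36 h) the ratio is 1.00.

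**Terminal half-life truly 25% shorter in B** (modelled as present for all 24 doses)
- Planned windows: ratio 0.78 to 1.54, median 0.98, at or above 1 in 12 of 27 scenarios. Mid-grid: 17.9 h in B against 17.6 h in A, ratio 1.02.
- Both treatments limited to 24 h: ratio 0.75 to 0.81, median 0.76. Mid-grid: 13.4 / 17.6 = 0.76.

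**Second grid.** A separate set of assumptions (terminal 12, 18, 24 or 36 h; f = 0.2 or 0.4) gave a ratio of 1.05 to 2.06 with the best-fit rule. With a common 7 to 24 h window and no drug effect it gave 1.00 throughout.

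**The case against.** **No formal comparison is planned.** Section 7.1.4.1 specifies ratios and 90% confidence intervals only for AUC(0-τ), Cτ and Cmax. The B/A ratio of t1/2 used above is not an output of the SAP. This is true and limits the weight of the point. But the objective covers EE/LNG alone and with GSK3640254, and the tables show the parameter by treatment, so readers will compare the two.

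**λz selection may be governed by working practices not shown.** Span or fit criteria there could leave poorly defined Treatment A half-lives unreported. That cannot be ruled out. Rules applied to each profile separately, however, would not in general align the windows between treatments.

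**The λz points are listed.** That lets a careful reader find the mismatch subject by subject. It does not correct the summary tables.

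**The size rests on assumed kinetics.** This stands. The range begins at 1.00, the bias is small if distribution is nearly complete by 7 h, and the median of a chosen grid is not an expected value.

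**A 24 h limit fixes only the end of the window.** In a simulation of the mid-grid case with 5 to 15% residual error, the fitted start point differed between A and B in 66 to 75% of simulated participants. The median ratio was still about 1.00, so the systematic bias is removed. The 24 h value also understates the terminal half-life, and a footnote alone would be cheaper. A footnote would warn the reader but would leave the SAP without a comparable A and B half-life.

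**Conclusion.** The concern holds. Followed as written, the SAP can produce a biased side-by-side display of EE and LNG half-life, and nothing in it corrects this or warns of it. The mismatch in sampling length is a fact of the document. The size of its effect is not known. It depends on two-phase decline and on quantifiable samples at 48 h, with or without 72 h. Where those conditions fail, the bias disappears.

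The consequence is confined to a descriptive secondary endpoint. AUC(0-τ), Cτ and Cmax use 0 to 24 h in both treatments, so the primary analysis and the lack-of-effect conclusion stand. The change should be made, but the study's main result does not depend on it.

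**What to change.** In Sections 7.2.1.2 and 7.2.4, state that for the Treatment A and B summary of EE and LNG t1/2 (Tables 3.7 to 3.10) λz is derived from samples up to and including 24 h post-dose in both treatments. Report t1/2 from the Day 21 0 to 72 h profile separately, for Treatment B only, with a footnote that it is not comparable with Treatment A.

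No new sampling is needed; Treatment A cannot be followed beyond 24 h because dosing continues on Day 11. The cost is one extra non-compartmental derivation on existing data, the SAP wording and a table footnote. The drawback is that the 24 h value is a comparison measure and may understate the terminal half-life (17.6 h against an assumed true 24 h in the mid-grid case). Keeping the 0 to 72 h value as a separate Treatment B parameter covers that.
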